7. SAFETY

The investigator or site staff is/are responsible for the detection, documentation and reporting of events meeting the criteria and definition of an adverse event (AE) or serious adverse event (SAE) as provided in this protocol.

Each subject will be instructed to contact the investigator immediately should they manifest any signs or symptoms they perceive as serious.

7.1. Safety definitions

7.1.1. Definition of an adverse event

An AE is any untoward medical occurrence in a clinical investigation subject, temporally associated with the use of a medicinal product, whether or not considered related to the medicinal product.

An AE can therefore be any unfavourable and unintended sign (including an abnormal laboratory finding), symptom, or disease (new or exacerbated) temporally associated with the use of a medicinal product. For marketed medicinal products, this also includes failure to produce expected benefits (i.e. lack of efficacy), abuse or misuse.

Examples of an AE include:

- Significant or unexpected worsening or exacerbation of the condition/indication under study.
- New conditions detected or diagnosed after investigational vaccine administration even though they may have been present prior to the start of the study.
- Signs, symptoms, or the clinical sequelae of a suspected interaction.
- Signs, symptoms, or the clinical sequelae of a suspected overdose of either investigational vaccine or a concurrent medication (overdose per se should not be reported as an AE/SAE).
- Signs, symptoms temporally associated with vaccine administration.
- Significant failure of expected pharmacological or biological action.
- Pre- or post-treatment events that occur as a result of protocol-mandated procedures (i.e. invasive procedures, modification of subject's previous therapeutic regimen).

AEs to be recorded as endpoints (solicited AEs) are described in Section 7.1.3. All other AEs will be recorded as UNSOLICITED AEs.

Examples of an AE DO NOT include:

- Medical or surgical procedures (e.g. endoscopy, appendectomy); the condition that leads to the procedure is an AE/SAE.
- Situations where an untoward medical occurrence did not occur (e.g. social and/or convenience admission to a hospital, admission for routine examination).
- Anticipated day-to-day fluctuations of pre-existing disease(s) or condition(s) present or detected at the start of the study that do not worsen.
- Pre-existing conditions or signs and/or symptoms present in a subject prior to the study vaccination. These events will be recorded in the medical history section of the eCRF.

7.1.2. Definition of a serious adverse event

A SAE is any untoward medical occurrence that:

- a. Results in death,
- b. Is life-threatening,

Note: The term 'life-threatening' in the definition of 'serious' refers to an event in which the subject was at risk of death at the time of the event. It does not refer to an event, which hypothetically might have caused death, had it been more severe.

- c. Requires hospitalisation or prolongation of existing hospitalisation,

Note: In general, hospitalisation signifies that the subject has been admitted at the hospital or emergency ward for observation and/or treatment that would not have been appropriate in the physician's office or in an out-patient setting. Complications that occur during hospitalisation are also considered AEs. If a complication prolongs hospitalisation or fulfils any other serious criteria, the event will also be considered serious. When in doubt as to whether 'hospitalisation' occurred or was necessary, the AE should be considered serious.

Hospitalisation for elective treatment of a pre-existing condition (known or diagnosed prior to informed consent signature) that did not worsen from baseline is NOT considered an AE.

- d. Results in disability/incapacity, OR

Note: The term disability means a substantial disruption of a person's ability to conduct normal life functions. This definition is not intended to include experiences of relatively minor medical significance such as uncomplicated headache, nausea, vomiting, diarrhoea, influenza like illness, and accidental trauma (e.g. sprained ankle) which may interfere or prevent everyday life functions but do not constitute a substantial disruption.

- e. Is a congenital anomaly/birth defect in the offspring of a study subject.

Medical or scientific judgement should be exercised in deciding whether reporting is appropriate in other situations, such as important medical events that may not be immediately life-threatening or result in death or hospitalisation but may jeopardise the subject or may require medical or surgical intervention to prevent one of the other outcomes listed in the above definition. These should also be considered serious. Examples of such events are invasive or malignant cancers, intensive treatment in an emergency room or at home for allergic bronchospasm, blood dyscrasias or convulsions that do not result in hospitalisation.

7.1.3. **Solicited adverse events**

7.1.3.1. **Solicited local (injection-site) adverse events**

The following local (injection-site) AEs will be solicited ([Table 13](#)):

Table 13 Solicited local adverse events

Pain at injection site
Redness at injection site
Swelling at injection site

7.1.3.2. **Solicited general adverse events**

The following general AEs will be solicited ([Table 14](#)):

Table 14 Solicited general adverse events

Fatigue
Fever
Gastrointestinal symptoms [†]
Headache

[†]Gastrointestinal symptoms include nausea, vomiting, diarrhoea and/or abdominal pain.

Note: Temperature will be preferably recorded in the evening. Should additional temperature measurements be performed at other times of day, the highest temperature will be recorded in the eCRF.

7.1.4. **Clinical laboratory parameters and other abnormal assessments qualifying as adverse events or serious adverse events**

In absence of diagnosis, abnormal laboratory findings (e.g. clinical chemistry, haematology, urinalysis) or other abnormal assessments (e.g. vital signs, etc.) that are judged by the investigator to be clinically significant will be recorded as AE or SAE if they meet the definition of an AE or SAE (refer to Sections [7.1.1](#) and [7.1.2](#)). Clinically significant abnormal laboratory findings or other abnormal assessments that are present at baseline and significantly worsen following the start of the study will also be reported as AEs or SAEs.

The investigator will exercise his or her medical and scientific judgement in deciding whether an abnormal laboratory finding or other abnormal assessment is clinically significant.

7.2. Events or outcomes not qualifying as adverse events or serious adverse events

7.2.1. Pregnancy

Female subjects who become pregnant after the vaccination may continue the study at the discretion of the investigator.

While pregnancy itself is not considered an AE or SAE, any adverse pregnancy outcome or complication or elective termination of a pregnancy for medical reasons will be recorded and reported as an AE or a SAE.

Note: The pregnancy itself should always be recorded on an electronic pregnancy report.

The following should always be considered as SAE and will be reported as described in Sections 7.4.1 and 7.4.3:

- Spontaneous pregnancy loss, including:
 - spontaneous abortion, (spontaneous pregnancy loss before/at 22 weeks of gestation)
 - ectopic and molar pregnancy
 - stillbirth (intrauterine death of foetus after 22 weeks of gestation).

Note: the 22 weeks cut-off in gestational age is based on WHO-ICD 10 noted in the EMA Guideline on pregnancy exposure [[EMA](#), 2006]. It is recognised that national regulations might be different.

- Any early neonatal death (i.e. death of a live born infant occurring within the first 7 days of life).
- Any congenital anomaly or birth defect (as per [[CDC MACDP](#)] guidelines) identified in the offspring of a study subject (either during pregnancy, at birth or later) regardless of whether the foetus is delivered dead or alive. This includes anomalies identified by prenatal ultrasound, amniocentesis or examination of the products of conception after elective or spontaneous abortion.

Furthermore, any SAE occurring as a result of a post-study pregnancy AND considered by the investigator to be reasonably related to the investigational vaccine will be reported to GSK Biologicals as described in Section 7.4.3. While the investigator is not obligated to actively seek this information from former study participants, he/she may learn of a pregnancy through spontaneous reporting.

7.3. Detecting and recording adverse events, serious adverse events and pregnancies**7.3.1. Time period for detecting and recording adverse events, serious adverse events and pregnancies**

All AEs following the administration of the dose of study vaccine (Day 0 to Day 30) must be recorded into the appropriate section of the eCRF, irrespective of intensity or whether or not they are considered vaccination related.

The time period for collecting and recording SAEs will begin at the receipt of study vaccine and will end 30 days following administration of the dose of study vaccine for each subject. See Section [7.4](#) for instructions on reporting of SAEs.

All AEs/SAEs leading to withdrawal from the study will be collected and recorded from the time of the receipt of study vaccine.

SAEs that are related to the investigational vaccine will be collected and recorded from the time of the receipt of study vaccine until the subject is discharged from the study.

In addition to the above-mentioned reporting requirements and in order to fulfil international reporting obligations, SAEs that are related to study participation (i.e. protocol-mandated procedures, invasive tests, a change from existing therapy) or are related to a concurrent GSK medication/vaccine will be collected and recorded from the time the subject consents to participate in the study until she/he is discharged from the study.

The time period for collecting and recording pregnancies will begin at the receipt of study vaccine and will end 30 days following administration of the dose of study vaccine. See section [7.4](#) for instructions on reporting of pregnancies.

An overview of the protocol-required reporting periods for AEs, SAEs, and pregnancies is given in [Table 15](#).

Table 15 Reporting periods for collecting safety information

Event	ICF sign off*	Visit 1 Vaccination	4 d (Days 0-3) post-vaccination	Visit 2	Visit 3 31 d (Days 0-30) post-vaccination Study Conclusion
		D0		D7	D30
Solicited local and general AEs					
Unsolicited AEs					
AEs/SAEs leading to withdrawal from the study					
SAEs related to the investigational vaccine					
SAEs related to study participation or concurrent GSK medication/vaccine					
Pregnancies					

* i.e. consent obtained. D: Day.

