3. STUDY DESIGN OVERVIEW

n = Total number of subjects, PRE = Blood sample to be collected before vaccination, PD7 = Blood sample to be collected 7 days after vaccination, PD30 = Blood sample to be collected 30 days after vaccination.

Protocol waivers or exemptions are not allowed with the exception of immediate safety concerns. Therefore, adherence to the study design requirements, including those specified in the outline of study procedures (Section 5.5), are essential and required for study conduct.

- Experimental design: Phase IV, open-label, non-randomised, multi-centric, multi-country study with a single group.
- Duration of the study: Approximately one month per subject, starting from the administration of the challenge dose.
 - Epoch 001: Primary starting at Visit 1 (Day 0) and ending at Visit 3 (Day 30).
- Study group:
 - LTFU: Subjects who received 3 or 4 doses of *Engerix-B* 20 to 30 years ago.

The study group and epoch foreseen in the study are provided in Table 1.

Table 1 Study group and epoch foreseen in the study

Study group	Number of subjects	Age (Min/Max)‡	Epoch
			Epoch 001
LTFU	Approximately 100	40 years - 60 years	x

‡ Age at vaccination.

The study group and treatment foreseen in the study are provided in Table 2.

Table 2 Study group and treatment foreseen in the study

Treatment name	Vaccine name	Study Group
		LTFU
Engerix-B	HBV	x

- Control: uncontrolled.
- Vaccination schedule: A single dose of *Engerix-B* will be administered to all subjects at Visit 1 (Day 0).
- Treatment allocation: Non-randomised.
- Blinding: Open-label.

Table 3 Blinding of study epoch

Study Epoch	Blinding
Epoch 001	open-label

- Sampling schedule: Blood samples will be taken from all subjects in order to evaluate the immunogenicity endpoints. The following blood samples will be taken at each study visit (Visit 1 [PRE], Visit 2 [PD7] and Visit 3 [PD30]):
 - Three heparinised tubes of whole blood, of approximately 9 ml each, will be sampled for the assessment of memory B cells and T cells.
 - One tube of approximately 5 ml of blood will be taken, from which approximately 1.7 ml of serum will be extracted for the measurement of antibodies.
- Type of study: self-contained
- Data collection: electronic Case Report Form (eCRF).

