Visit 1→ Visit 2	7 days	5 days - 12 days
Visit 1→ Visit 3	30 days	21 days - 48 days

¹ Subjects will not be eligible for inclusion in the ATP cohort for analysis of immunogenicity if they make the study visit outside this interval.

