9.2. Secondary endpoints

- Persistence of immunity to hepatitis B in adult subjects vaccinated with three or four doses of *Engerix-B* 20 to 30 years ago.
 - Percentage of adult subjects with anti-HBs antibody concentrations ≥ 6.2 mIU/ml, ≥ 10 mIU/ml and ≥ 100 mIU/ml, at the pre-challenge dose time-point and Day 7 and Day 30 post-challenge dose time-points.
 - Anti-HBs antibody concentrations, at the pre-challenge dose time-point and Day 7 and Day 30 post-challenge dose time-points.
 - Hepatitis B specific memory B cell-mediated immune responses (frequency of HBs-specific memory B cells) at the pre-challenge dose time-point and Day 7 and Day 30 post-challenge dose time-points.
 - Hepatitis B specific T cell-mediated immune responses (frequency of HBs-specific CD4 T-lymphocytes) at the pre-challenge dose time-point and Day 7 and Day 30 post-challenge dose time-points.
- Solicited local and general symptoms.
 - Occurrence of solicited local symptoms during the 4-day (Days 0-3) follow-up period after the challenge dose.
 - Occurrence of solicited general symptoms during the 4-day (Days 0-3) follow-up period after the challenge dose.

- Unsolicited adverse events.
 - Occurrence of unsolicited symptoms during the 31-day (Days 0-30) follow-up period after the challenge dose.
- Serious adverse events.
 - Occurrence of SAEs after the challenge dose, up to the study end.

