9.9. Analysis of safety

The primary analysis will be performed on the TVC.

- The percentage of subjects who reported at least one local AE (solicited and unsolicited), with at least one general AE (solicited and unsolicited) and with any AE during the 4-day (Days 0-3) follow-up period after the vaccination will be tabulated with exact 95% CI. The same calculations will be performed for any Grade 3 (solicited or unsolicited) symptoms and any symptoms requiring medical attention.
- The percentage of subjects reporting each individual solicited symptom during the 4-day (Days 0-3) follow-up period with exact 95% CI, by type of AE; by severity (any Grade, Grade 3 only); by relationship to vaccination (any relationship, related only) will be tabulated.
- The occurrence of fever will be tabulated per 0.5°C cumulative increments as well as the occurrence of Grade 3 fever (> 39.0 °C axillary temperature) with causal relationship to vaccination.
- The percentage of subjects reporting at least one report of unsolicited AE classified by the Medical Dictionary for Regulatory Activities (MedDRA) and reported within the 31-day (Days 0-30) follow-up period after vaccination will be tabulated with exact 95% CI. The same tabulation will be performed for Grade 3 unsolicited AEs and for unsolicited AEs with a causal relationship to vaccination.
- SAEs during the entire study period and withdrawals due to AEs and SAEs reported during the 31-day follow-up period after the challenge dose will be described in detail.

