| | Related | | | | |
| | >39.0 Related | | | | |
| | Medical advice | | | | |

HBV : Engerix-B challenge dose

N = number of subjects with documented dose

n/% = number/percentage of subjects reporting the symptom at least once

95%CI = Exact 95% confidence interval; LL = lower limit, UL = upper limit

Template 26 Percentage of subjects reporting the occurrence of unsolicited symptoms classified by MedDRA Primary System Organ Class and Preferred Term within the 31-day (Days 0-30) post-vaccination period (Total Vaccinated Cohort)

| Primary System Organ Class (CODE) | Preferred Term (CODE) | HBV group N =XXX | | | |
|---|--------------------------------|---------------------|--|--|--|
| | | 95% CI | | | |
| At least one symptom | | | | | |
| Blood and lymphatic system disorders (10005329) | Anaemia (10002034) | | | | |
| | Hypochromic anaemia (10020969) | | | | |
| | Thrombocytopenia (10043554) | | | | |
| Immune system disorders (10021428) | Milk allergy (10027633) | | | | |
| Infections and infestations (10021881) | Bronchiolitis (10006448) | | | | |
| | Bronchitis (10006451) | | | | |
| | Gastroenteritis (10017888) | | | | |
| | Rash (10037844) | | | | |

HBV : Engerix-B challenge dose

At least one symptom = at least one symptom experienced (regardless of the MedDRA Preferred Term)

N = number of subjects with at least one administered dose

n/% = number/percentage of subjects reporting the symptom at least once

95% CI= exact 95% confidence interval; LL = Lower Limit, UL = Upper Limit

Template 27 Incidence of concomitant medication during the 4-day (Days 0-3) post-vaccination period (Total vaccinated cohort)

| | HBV group | | | 95% CI | |
|--------------------------|-----------|---|---|--------|----|
| | N | n | % | LL | UL |
| | | | | | |
| Any | | | | | |
| Any antipyretic | | | | | |
| Prophylactic antipyretic | | | | | |

HBV : Engerix-B challenge dose

95% CI = exact 95% confidence interval, LL = Lower Limit, UL = Upper Limit

Template 28 Number (%) of subjects reporting serious adverse events during the whole study period including number of events reported (Total vaccinated cohort)

| Type of Event | Primary System Organ Class | Preferred Term (CODE) | HBV group N = | | |
|-------------------|----------------------------|-----------------------|------------------|---|---|
| | | | n* | n | % |
| SAE | At least one symptom | | | | |
| | <each SOC> | <each PT term> | | | |
| Related SAE | At least one symptom | | | | |

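### All-causality SAE collection ends 30 days after the dose, but the SAE endpoint and tables run to study end, which may fall anywhere from Day 21 to Day 48

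*Protocol*

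**What the plan says.** **Collection.** Under Protocol 7.3.1, recording of SAEs in general starts at the dose and "will end 30 days following administration of the dose of study vaccine for each subject". Three further rules in that section reach beyond this or set no end:

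- Vaccine-related SAEs are collected from the dose until discharge from the study.
- SAEs related to study participation or to a concurrent sponsor product are collected from consent until discharge.
- AEs and SAEs leading to withdrawal are collected from the dose, whatever their causality, with no stated end.

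Table 5 (Protocol 5.5) has an eCRF-documented row for recording SAEs at Visits 1, 2 and 3. It carries no day limit, whereas the row for non-serious AEs is limited to Days 0-30.

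**Endpoint and analysis.** The secondary endpoint (synopsis and Protocol 9.2) is "Occurrence of SAEs after the challenge dose, up to the study end". Protocol 9.9, repeated in SAP 6.4.1, will describe "SAEs during the entire study period and withdrawals due to AEs and SAEs reported during the 31-day follow-up period". SAP Template 28 is titled "Number (%) of subjects reporting serious adverse events during the whole study period including number of events reported" and has separate rows for SAEs, related SAEs, fatal SAEs and related fatal SAEs.

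**Study end.** Protocol 8.1 treats a subject as having completed the study on returning for the concluding visit, which is Visit 3. Protocol 3 places it nominally at Day 30. Table 6 gives 30 days as the optimal interval from Visit 1 and allows "21 days - 48 days".

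**The concern.** The endpoint, the analysis text and the table each claim a period that the collection rule does not guarantee. Suppose Visit 3 is on Day 45 and an unrelated SAE, not leading to withdrawal, starts on Day 40. The endpoint counts it. Section 7.3.1 does not ask for it. Table 5 appears to ask for it. A site has no single rule to follow, and two sites could handle the same event differently.

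In the final table, the Related SAE row would hold events up to discharge. The SAE row would be complete only to Day 30, plus whichever later events happened to qualify. Both rows sit under one title that says the whole study. A reader would take an SAE percentage as complete over a period in which some SAEs were not sought.

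The opposite case is also open. A Visit 3 on Days 21-29 ends the study while the 30-day collection window is still running, and the plan specifies no later contact to close it.

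**Working it through.** **Inputs**

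- End of all-causality SAE collection: Day 30 (Protocol 7.3.1).
- Visit 3: optimal Day 30, allowed Days 21 to 48 (Table 6).
- Safety follow-up: 31 days, Days 0-30 (Protocol 9.2).
- Enrolment: approximately 100 (Protocol 4.1).

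**The plan's own figure.** Days 0 to 30 inclusive: 30 − 0 + 1 = 31 days, as stated.

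**Are Day 30 and study end meant to be the same?** The text keeps them apart in four places:

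| Place | Day 30 period | Study-end period |
|---|---|---|
| Protocol 7.3.1 | All SAEs | Related SAEs, to discharge |
| Protocol 7.5.1.1 | Follow-up of AEs | Follow-up of SAEs |
| Protocol 9.2 | Unsolicited symptoms | SAEs |
| Protocol 9.9 | Withdrawals due to AEs and SAEs | SAEs |

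Continuing related SAEs to discharge adds nothing after the dose if discharge is always Day 30. Study end therefore cannot be read simply as another name for Day 30.

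**Late Visit 3**

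- Longest tail within the allowed window: 48 − 30 = 18 days (Days 31-48).
- As a share of Days 0-48 (49 days): 18/49 = 36.7%.

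**Early Visit 3**

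- Longest shortfall: 30 − 21 = 9 days (Days 22-30). Shortest: 30 − 29 = 1 day.

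**Allowed Visit 3 days.** 48 − 21 + 1 = 28 days: 9 before Day 30 (21-29), 1 on Day 30 and 18 after it (31-48). These are counts of calendar days, not of subjects.

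**Person-days in the late tail.** Formula: 100 × share of subjects with a late Visit 3 × mean tail in days. The documents give no distribution of visit dates, so both factors are assumptions.

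| Share late | Mean tail | Person-days |
|---|---|---|
| 10% | 3 days | 100 × 0.10 × 3 = 30 |
| 25% | 9 days | 100 × 0.25 × 9 = 225 |
| 50% | 18 days | 100 × 0.50 × 18 = 900 |
| 100% (bound within the window) | 18 days | 100 × 1.00 × 18 = 1,800 |

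The tail is zero for every subject whose Visit 3 is on or before Day 30.

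**What is collected in the late tail (Day 31 to discharge)**

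| Event | In the endpoint? | Collected under 7.3.1? |
|---|---|---|
| SAE related to the vaccine | Yes | Yes |
| SAE related to study participation or a concurrent sponsor product | Yes | Yes |
| Unrelated SAE leading to withdrawal | Yes | Yes (no end stated) |
| Other unrelated SAE | Yes | No |

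The mismatch at the late end is confined to the last row.

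**The case against.** The best defence is that the plan treats Visit 3, Day 30 and study conclusion as one time-point. Epoch 001 ends at Visit 3 on Day 30, and the header of Table 15 groups the three. On schedule, the endpoint and collection coincide. Table 5 asks for SAEs at Visit 3 without a cut-off, the question suggested in Protocol 7.3.3.1 refers to the time since the previous visit, and Protocol 7.4.3 requires a report once the investigator learns of an SAE in a study subject. In practice a late unrelated SAE may well be recorded.

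Much of this stands. It makes the problem an ambiguity between sections rather than a demonstrated loss of data. It does not remove the ambiguity: Protocol 7.4.1 ties prompt reporting to the period in 7.3, Protocol 7.3.2 calls events outside the Table 15 period post-study, and the allowed visit window makes departures from Day 30 an expected part of the design. The reporting bars of Table 15 are not legible in the available text, so nothing is inferred from its cells.

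A reader might also infer stronger claims, which the documents do not support:

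- **That the SAE endpoint is not collected.** SAEs of any causality are collected to Day 30, and the endpoint is fully covered when Visit 3 is on or before that day.
- **That only related SAEs are kept after Day 30.** SAEs leading to withdrawal are kept whatever their causality.
- **That the proportion of SAEs judged related is inflated.** No such proportion is planned. Each Template 28 row uses all dosed subjects as its denominator. What remains is that two adjacent rows can cover different periods.
- **That about 64% of subjects have a late tail.** 18/28 = 0.64 follows only if visit dates are uniform over Days 21-48. The documents give no such distribution, and the optimal day is 30.
- **That Day 48 is the latest possible study end.** Table 6 attaches only one consequence: "Subjects will not be eligible for inclusion in the ATP cohort for analysis of immunogenicity if they make the study visit outside this interval". A later Visit 3 is still a concluding visit.

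**Conclusion.** The inconsistency is real and narrow. The collection window and the endpoint period agree only for a Visit 3 on Day 30. After that, up to 18 days within the allowed window fall inside the endpoint, yet 7.3.1 does not collect unrelated SAEs that do not lead to withdrawal. Before that, the study ends up to 9 days short of the collection window.

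The practical size is small. The documents give no SAE rate, so no event count is computed. The expectation of few events is a judgement, resting on about 100 adults and a tail of at most 1,800 person-days if every Visit 3 falls within its window. All analyses are descriptive (Protocol 9.10, SAP 7), and no sample size, confidence level or immunogenicity result changes. The point concerns a listed secondary endpoint whose period should be stated once and followed everywhere.

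**What to change.** Reconcile the passages in one of two ways.

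1. **Extend collection.** State in Protocol 7.3.1 and Table 15 that all SAEs, whatever their causality, are recorded from the dose to the study conclusion visit. This matches Table 5 and leaves the endpoint and Template 28 as they are. Late events can be captured at Visit 3, so that tail needs no extra contact. The option works only while subjects are still in follow-up.
2. **Restrict the endpoint.** Restate the endpoint (synopsis and Protocol 9.2), Protocol 9.9, SAP 6.4.1 and Template 28 as Days 0-30, and list any later SAEs separately with the rule under which they were collected. All rows of Template 28 then cover the same nominal period.

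In either case, state the period covered for subjects whose Visit 3 is before Day 30. The choice is between ending at that visit, with the shorter follow-up made visible in a footnote, and completing the 30 days. The second would need a contact after Visit 3, which the plan does not currently provide.

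The cost is wording in a few sections and one table title or footnote, plus that contact if the full 30 days is wanted for everyone.
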